[figure not shown]
Final

Clinical Evaluation of clariti Monthly Toric and clariti® 1 day Toric

Sponsor Study Code:	EX-MKTG-137
Protocol Date:	June 16, 2022
Sponsor Company:	CooperVision, Inc.
Document Type:	Protocol
Study Category:	Post Market
Start Date:	July 2022
Finish Date:	September 2022
Clinical Site:	School of Optometry Clinic, National Autonomous University (UNAM), Mexico City

Revision History

Document number	Date	Comments
EX-MKTG-137	6/16/2022	First draft (v 1.0)
EX-MKTG-137	6/16/2022	FINAL

Protocol Synopsis

Protocol Number	EX-MKTG-137
Title	Clinical Evaluation of clariti Monthly Toric and clariti® 1 day Multifocal.
Name of Device(s) and (by USAN material)	Clariti Monthly Toric (somofilcon A), clariti 1-Day Toric (somofilcon A)
Indications for Use	
Approved for use:
 
 • somofilcon A. (Daily wear) • somofilcon A. (Daily wear) 
Indication for use in this study:
 
 • 15 minutes daily wear
Study Design	Subject masked, interventional, prospective, direct refit, bilateral wear study.
Purpose	The aim of this non-dispensing fitting study is to evaluate the short term lens fit, vision performance and patient subjective experiences of the Clariti Monthly Toric when compared to the Clariti 1-Day Toric after 15 minutes of daily wear.
Study Duration	
The anticipated timeline for this study is as follows:
 
 • Patient enrolment and completion: July 15 - Sept 15, 2022 Visits: V1: (BL/trial fit/lens order), V2: Dispense / evaluate P1 V3: 15 minutes. Evaluate P1/Dispense P2. V4: 15 minutes. Evaluate P2 / study exit
Patient Population	Habitual soft toric contact lens wearers who provide written informed consent and meet the protocol entrance criteria.
Sample Size	Target enrollment and completion is 37- 40 subjects.
Center Destination (Mexico)	School of Optometry Clinic, National Autonomous University (UNAM)
Number of Centers	Single Center
Patient Follow-up	
Subjects enrolled in this study will be followed up after the lens dispensing session:
 
 • Post dispensing follow-up at 15 minutes for each study lens pair
Primary Endpoint	Subjective handling (insertion & removal)

Table of Contents

1	Introduction	6
2	Study Objective	6
3	Study Hypothesis	6
3.1	Study Hypothesis	6
4	Study Design	7
5	Investigational Sites	7
5.1	Number of Sites	7
5.2	Investigator Recruitment	7
6	Ethics Review / Statement of Compliance	7

The aim of this non-dispensing fitting study is to evaluate the short term lens fit, vision performance and patient subjective experiences of the Clariti Monthly Toric when compared to the Clariti 1-Day Toric after 15 minutes of daily wear.

The primary outcome variable is:

- Subjective handling ratings on insertion (assessed by subjects)

3 Study Hypothesis

3.1 Study Hypothesis

- Null hypothesis (Ho): There is no difference in clinical performance and subjective assessments between toric lens types.
- Alternative hypothesis (H1): There is a difference in clinical performance and subjective assessments between toric lens types.

4 Study Design

This is a subject masked, interventional, prospective, direct refit, bilateral wear study. It is anticipated that this study will involve 4 visits as follows: **V1:** (BL/trial fit/lens order), **V2:** Dispense / evaluate P1. **V3:** 15 minutes. Evaluate P1/Dispense P2. **V4:** 15 minutes. Evaluate P2 / study exit.

5 Investigational Sites

5.1 Number of Sites

This will be a single center investigational site in Mexico City. (Target 37- 40 subjects).

5.2 Investigator Recruitment

This study will be conducted at School of Optometry Clinic; National Autonomous University (UNAM) Mexico City. The Investigators will be required to fulfil the following criteria:

- Licensed optometrist with at least two years of contact lens fitting experience.
- Experienced Investigators who will be trained in Good Clinical Practice (GCP) by the principal investigator.
- In-office email or fax.
- Willingness to follow the study protocol and to co-operate with the study monitors.

This clinical study is designed to be in conformance with the ethical principles in the Declaration of Helsinki, with the ICH guidelines for Good Clinical Practice (GCP) and all the applicable local guidelines.

6 Ethics Review / Statement of Compliance

6.1 Relevant Standards / Guidelines

This implementation document has been developed in accordance with the following:

- ISO 14155. Clinical Investigation of Medical Devices
- ICH Harmonized Tripartite Guideline for Good Clinical Practice
- Declaration of Helsinki

6.2 Institutional Review Board

This study will be conducted in accordance with Institutional Review Board regulations (U.S. 21CFR Part 56.103) or applicable IEC regulations. Copies of all IRB/IEC correspondence with the investigator/sponsor will be kept on file. The study will commence upon approval from the following Ethics Committee: Comisión de Ética de la FESI. [name]. [contact] and email address [contact].

6.3 Clinical Trial Registration

This study will be registered with clinical trials.gov in accordance with section 801 of the Food and Drug Administration (FDA) Act which mandates the registration of certain clinical trials of drugs and medical devices.

6.4 Informed Consent

Informed consent, (Appendix 1), shall be obtained in writing from the subject and the process shall be documented before any procedure specific to the clinical investigation is carried out.

7 Potential Risks and Benefits to Human Subjects

There may be direct benefits to the subjects in this study such as improved vision, comfort, convenience, and cosmetic advantage. Participation in a study may contribute to scientific research information that may be used in the development of new contact lens products. In addition, subjects will receive an examination of the front part of their eyes and may have the opportunity to try a different type of soft contact lenses and/or different lens care products at no cost to them. The contact lens materials used in this study are commercially available intended for daily wear (NOT extended wear) similar to the average wearing time of 10-16 hours for daily wear lenses.

This study is considered to be a non-significant risk study based on United State Food and Drug administration (FDA) and International Standards Organization (ISO) guidelines because the study devices used as intended in this study (daily wear) don't represent a potential for serious risk to the health, safety or welfare of the subject, and (2) it is not an implant, (3) it is not used to support or sustain human life, (4) it is not of substantial importance in diagnosing, curing, mitigating or treating disease or otherwise prevents impairment of human health, (5) does not present a potential for serious risk to the health, safety or welfare of the subject.

Complications that may occur during the wearing of contact lenses include discomfort, dryness, aching or itching eyes, excessive tearing, discharge, hyperemia and variable or blurred vision. More serious risks may include photophobia, iritis, corneal edema or eye infection. Although contact lens-related infections are very infrequent, the possibility does exist. The incidence of infection due to day-wear soft lenses is 0.035%. Almost always an infection will occur only in one eye. This risk is assumed by 35-million Americans who currently wear contact lenses. Routine clinical procedures including auto-refraction, auto-keratometry, visual acuity, anterior ocular health assessment, and contact lens fitting will be used. In addition, high magnification imaging of the lens fit may be made using 35 mm or digital cameras, in vivo confocal microscopy, and/or specular microscopy. Patients will be monitored in the clinic during the study to reduce if not eliminate the occurrence of adverse or potential adverse events. Patients will be given instructions from the study investigator regarding early symptoms and signs of adverse events and their contact information.

8 Materials and Methods

8.1 Participants

Habitual soft toric contact lens wearers that provide written informed consent and meet the protocol entrance criteria. Subjects will be recruited from the National Autonomous University School of Optometry databases who agree to voluntarily participate in the study (Appendix 2, timeline). All subjects will be screened to determine study eligibility. Each subject will be given a unique ID number. Additionally, all subjects must meet the study inclusion and exclusion criteria listed below.

Inclusion criteria

A person is eligible for inclusion in the study if he/she:

- A person is eligible for inclusion in the study if he/she:
- Is between 18 and 40 years of age (inclusive)
- Has had a self-reported visual exam in the last two years
- Is an adapted soft contact lens wearer
- Is not a habitual wearer of either study lens
- Has a contact lens spherical prescription between +4.00 to - 9.00 (inclusive) best corrected visual acuity of 20/30 or better in either eye
- Have contact lens prescription of no less than -0.75D of astigmatism and no more than -2.25 D in both eyes.
- Can achieve best corrected spectacle distance visual acuity of 20/25 (0.10 logMAR) or better in each eye.
- Can achieve a distance visual acuity of 20/30 (0.18 logMAR) or better in each eye with the study contact lenses.
- Has clear corneas and no active ocular disease
- Has read, understood and signed the information consent letter.
- Patient contact lens refraction should fit within the available parameters of the study lenses.
- Is willing to comply with the wear schedule (at least 5 days per week, > 8 hours/day assuming there are no contraindications for doing so).
- Is willing to comply with the visit schedule

Exclusion Criteria

A person will be excluded from the study if he/she:

- A person was excluded from the study if he/she:
- Has a CL prescription outside the range of the available parameters of the study lenses.
- Has a spectacle cylinder less than -0.75D or more than -2.50 D of cylinder in either eye.

- Has a history of not achieving comfortable CL wear (5 days per week; > 8 hours/day)
- Has contact lens best corrected distance vision worse than 20/25 (0.10 logMAR) in either eye.
- Presence of clinically significant (grade 2-4) anterior segment abnormalities
- Presence of ocular or systemic disease or need of medications which might interfere with contact lens wear.
- Slit lamp findings that would contraindicate contact lens wear such as:
 - Pathological dry eye or associated findings
 - Pterygium, pinguecula, or corneal scars within the visual axis
 - Neovascularization > 0.75 mm in front of the limbus
 - Giant papillary conjunctivitis (GCP) worse than grade 1
 - Anterior uveitis or iritis (past or present)
 - Seborrheic eczema, Seborrheic conjunctivitis
 - History of corneal ulcers or fungal infections
 - Poor personal hygiene
 - Has a known history of corneal hypoesthesia (reduced corneal sensitivity)
 - Has aphakia, keratoconus or a highly irregular cornea.
 - Has Presbyopia or has dependence on spectacles for near work over the contact lenses.
 - Has undergone corneal refractive surgery.
 - Is participating in any other type of eye related clinical or research study.

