8.3.1 Visit 1: Baseline / Trial Fit / Lens order

- Subjects should attend this visit wearing their **spectacle** lenses
- Explanation of the study.
- Sign informed consent form.
- Collect habitual toric lens brand information
 - Brand
 - Power(s)
 - Replacement schedule (daily, 2-week, monthly)
- Anterior ocular health examination (Slit lamp without fluorescein).
- Insert trial toric **LENS A**, evaluate the fit and optimize the prescription if needed.
- [REDACTED]
- [REDACTED]
- Order final **LENS A**.
- Remove **LENS A** and insert trial toric **LENS B**. Evaluate fit and optimize the prescription if needed.
- [REDACTED]
- [REDACTED]
- Order final **LENS B**.

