10.2 Sample size

Figure 1 shows the sample size determination for a paired t-test, ($\alpha=0.05$), in order to detect a difference in mean subjective handling scores between lenses. Assuming a standard deviation of 1.2, a sample size of about 37 completed subjects provides 84% power to detect a difference in subjective handling ratings of 0.6 points on a 0 - 10 scale. In order to account for potential subject dropouts or AEs, 10%-15% should be added to the sample size. Therefore, 40 subjects should be enrolled with the aim to complete 37.

Figure 1. Sample size calculation (Minitab 20.2. Statistics software)

Paired t Test

Testing mean paired difference = 0 (versus ≠ 0)

Calculating power for mean paired difference = difference

$\alpha = 0.05$ Assumed standard deviation of paired differences = 1.2

Results

Difference	Sample Size	Target Power	Actual Power
0.6	34	0.80	0.807778
0.6	37	0.84	0.841192
0.6	44	0.90	0.900031

11 Data Quality Assurance

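### Do the 20/30 and 20/25 contact-lens acuity limits in Section 8.1 make the same subject both eligible and ineligible?

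*Combined protocol and SAP*

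**What the plan says.** Four bullets in Section 8.1 of the protocol set acuity limits.

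- Inclusion, study lenses: "Can achieve a distance visual acuity of 20/30 (0.18 logMAR) or better in each eye with the study contact lenses".
- Inclusion, attached without a connecting word to the contact-lens sphere range: "best corrected visual acuity of 20/30 or better in either eye". It names no correction and gives no logMAR value.
- Inclusion, spectacles: "Can achieve best corrected spectacle distance visual acuity of 20/25 (0.10 logMAR) or better in each eye".
- Exclusion: "Has contact lens best corrected distance vision worse than 20/25 (0.10 logMAR) in either eye".

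The opening paragraph of the section says how the lists combine: "all subjects must meet the study inclusion and exclusion criteria listed below". At Visit 1 (Section 8.3.1), "Subjects should attend this visit wearing their spectacle lenses". Both study lenses are then trial-fitted in turn, and some items after each trial fit are redacted.

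**The concern.** The study-lens inclusion and the contact-lens exclusion both concern distance acuity in contact lenses, and they carry different limits almost one chart line apart. If they describe the same measurement, a candidate at 20/30 meets the inclusion bullet and triggers the exclusion bullet. The sphere-range bullet adds to the confusion: it says *either* eye where the other inclusion bullets say *each* eye, so one good eye would satisfy it.

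Three things could be at stake. Vision performance is part of the stated aim (Section 2), and an acuity limit decides which part of the range can be observed. A stricter limit might remove subjects who see slightly worse in one study lens and so shrink a real difference between lenses. And the investigators are unmasked (Section 8.2.6), so a choice between two rules at screening would be made by someone who knows which lens is on the eye.

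**Working it through.** **Inputs.** The limits are 20/25 (0.10 logMAR) and 20/30 (0.18 logMAR), from Section 8.1. The power inputs are from Section 10.2: difference 0.6, standard deviation of paired differences 1.2, two-sided alpha 0.05, 37 completers.

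**Step 1: the stated logMAR values.** logMAR = log10(denominator / 20).

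- 20/25: log10(1.25) = 0.0969, stated as 0.10.
- 20/30: log10(1.5) = 0.1761, stated as 0.18.

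Both reproduce on rounding. The gap is 0.18 − 0.10 = 0.08 logMAR.

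**Step 2: one measurement.** Suppose both bullets refer to the same contact-lens acuity, checked in steps of 0.02 logMAR.

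| Acuity (logMAR) | Inclusion (≤ 0.18) | Exclusion (> 0.10) | Outcome |
|---|---|---|---|
| 0.00 to 0.10 | met | not triggered | passes |
| 0.12 to 0.18 | met | triggered | excluded |
| 0.20 and 0.22 | not met | triggered | excluded |

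Since both lists apply, every row has exactly one outcome. Meeting one inclusion bullet does not make a person eligible. The effective limit is the smaller of 0.10 and 0.18, which is 0.10, and the 20/30 figure is redundant.

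**Step 3: two measurements.** Let X be best-corrected contact-lens acuity and Y the acuity achieved in the fitted study lens. The rule becomes X ≤ 0.10 and Y ≤ 0.18, and both limits operate. This is coherent. Table 1 gives the study lenses in four cylinder powers and 10° axis steps, so a stock lens can leave some error uncorrected and Y can be worse than X. The 20/25 figure for X would also match the spectacle bullet.

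The two readings give different answers only for subjects with X ≤ 0.10 and Y worse than 0.10 but no worse than 0.18. The documents do not say how many candidates that is.

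**Step 4: the *either eye* wording.** A subject with one good eye would pass the sphere-range bullet. The spectacle bullet (20/25) and the study-lens bullet (20/30) each require the limit in each eye, so the same subject fails both whenever the weaker eye falls short. The looser wording admits nobody. In the exclusion, *either eye* is the right form, because one failing eye is enough. Changing it to *each eye* would mean that both eyes had to fail before anyone was excluded.

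**Step 5: the primary analysis.** The plan states that "a sample size of about 37 completed subjects provides 84% power to detect a difference in subjective handling ratings of 0.6 points". The noncentrality is (0.6 / 1.2) × √37 = 3.04. Two-sided power from the noncentral t distribution on 36 degrees of freedom is 0.8412, against 0.841192 in Figure 1. No acuity figure enters this calculation.

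**The case for a change.** The strongest case for a change is that the protocol states a limit it may never apply. The exclusion names contact-lens vision, so the spectacle criterion does not explain it. Nothing visible says that it means habitual lenses or over-refraction: subjects arrive in spectacles, and the visible habitual-lens items are brand, power and replacement schedule. A reader cannot tell which population was intended, and the repair is a few words.

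Part of this stands. The measurement behind the exclusion is not defined in Section 8.1, and the two-measurement reading is an inference. But redacted items follow each trial fit, just where study-lens acuity could be recorded, and the procedures and case report forms (Appendices 5 and 6) are not available here. The missing detail cannot be counted against the plan.

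The consequences are weaker than the textual point.

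- **Compression of a lens difference.** This assumes that the exclusion is measured in the study lenses, which is the very thing left unstated. A limit of 20/30 would truncate the range as well. No size of effect is shown.
- **Unmasked screening.** Every participant wears both lenses (Section 8.3), so an eligibility decision cannot unbalance two groups. It can only alter who is enrolled.
- **Two inclusion bullets at 20/30.** Only the study-lens bullet names contact-lens acuity outright. Reading the sphere-range bullet the same way is natural, but the text does not say it.

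**Conclusion.** No change to the plan follows. The two figures differ, and they overlap over 0.08 logMAR if they describe one measurement. Even then the rule has a single outcome, because the inclusion and exclusion lists must both be satisfied. If they describe two measurements, there is no conflict. What remains is a gap in wording that screening staff can fill sensibly, plus a slip in the sphere-range bullet that has no effect.

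The primary comparison is a within-subject handling rating, and its 84% power at 37 completers is untouched. The limits could affect which subjects enter the vision comparisons, but the documents give no figure from which to size that, and no bias between lenses has been shown.

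This conclusion rests on the usual reading that a triggered exclusion prevails, and on one reading being applied to all candidates. It takes no position on which acuity limit is the right one.

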8.2 Study Materials

8.2.1 Contact lens

CooperVision will provide the site with an inventory of both study lenses (**LENS A**) and (**LENS B**) to allow participants to be fit with the lens powers available for this study.

All subjects will be trial fitted and, if suitable, dispensed the first pair of the assigned lens brand assigned per a determined table (Appendix 3). The lenses used in this study are all FDA approved and marketed products. Details of the study contact lenses are shown in Table1.

Table1: Study lens parameters

Brand	Clariti Monthly Toric (LENS A)	Clariti 1-Day Toric (LENS B)
Manufacturer	CooperVision	CooperVision
Material	somofilcon A	somofilcon A
FDA Class	Group 5	Group 5
WC %	56%	56%
Base Curve (mm)	8.7	8.6
Lens Diameter (mm)	14.4	14.3
Sphere Power (D)	+4.00D to -9.00D (0.50D steps after -8.50D)	Plano to -6.00 (0.25 steps) -6.50 to -9.00 (0.50 steps) +0.25D to +4.00D. (0.25D steps)
Cyl Power (D)	-0.75, -1.25, -1.75, -2.25	-0.75, -1.25, -1.75, -2.25
Axis (degrees)	10° to 180° (10° steps)	10° to 180° (10° steps)
Wearing schedule	Daily wear	Daily wear

8.2.2 Contact Lens care

OPTI-FREE® PureMoist® multipurpose disinfecting solution and lens cases (Alcon, Fort Worth, TX) will be provided to all subjects for care and maintenance of the contact lenses during the study.

8.2.3 Storage of Study Medications/Treatments

There are no unapproved investigational products used in this study requiring special storage accommodations.

8.2.4 Clinical Supply Inventory

There are no unapproved investigational products used in this study requiring special inventory requirements.

8.2.5 Disposal of Consumables

This study dispenses consumables (lenses) to participants for use during the study. Study lenses worn by participants will be discarded by the principal investigator at the end of the study.

8.2.6 Masking and Control of Study Materials

The contact lenses, (LENS A, and LENS B), will be masked to the subject only. The lenses will be removed from their blister pack by an assistant and transferred to an unmarked lens case to maintain the participants masked of the study lenses. Participants will then be instructed to remove the lenses from the lens case and insert them onto their eyes. It is not possible for the study investigators to be

masked because of the need to follow the specific lens fitting guide during the lens prescription optimization visit.

8.2.7 Ordering and Accountability of Study Materials

The study sponsor will supply the investigators with the study lenses to use during the study.

8.3 Visit Schedule and Procedures

This will be an interventional, subject masked, bilateral, non-dispensing fitting study. Participants will be examined at two different points over the course of one day, V1 (lens dispensing), V2 (15 minutes post lens settling). Participants will wear two different pairs of lenses with **LENS A** fitted first to all participants, followed by **LENS B**. Anterior ocular health examination will be performed at baseline without the use of fluorescein*.

** Fluorescein will not be used before lens dispensing to prevent potential eye discomfort that could influence subjective comfort ratings after lens fitting and settling. However, fluorescein will be instilled at the last visit upon lens removal.*

The following outline identifies the two study visits and the general procedures, (Appendix 5), to be conducted at each visit for each day of the study and recorded in the case report forms (Appendix 6):

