8.3.2 Visit 2: Lens dispensing (Fit LENS A / Evaluate)

- Subjective assessments
 - Handling on insertion (0 -10 scale).
 - [REDACTED]
 - [REDACTED]
 - [REDACTED])
- [REDACTED]
 - [REDACTED]
 - [REDACTED]
 - [REDACTED]
 - [REDACTED] [REDACTED]
 - [REDACTED]
 - [REDACTED] [REDACTED]
 - [REDACTED]

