8.3.3 Visit 3: [REDACTED] (Evaluate LENs A)

8.3.4 Visit 3: Lens dispensing (Fit LENS B / Evaluate)

- Subjective assessments
 - Handling on insertion (0 -10 scale).
 - [REDACTED]
 - [REDACTED]
 - [REDACTED]

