10.1 Statistical analysis

Summary statistics will be produced, (e.g., mean, standard deviation), by the principal investigator ([name]). Differences between lenses will be compared using Paired t-tests. Paired t-tests /analysis of variance for normal (interval/continuous) data, Wilcoxon's signed ranks test for non-normal (ordinal) data, chi-squares test for nominal data. A Chi-Square test will be used to evaluate lens preference questions. All participants who are evaluated in the study will be used in the analysis. In the event of missing data individual number of points will be excluded in the analysis and not extrapolated from the collected data. The critical alpha level for statistical significance will be set at $p \leq 0.05$, with adjustment for multiple comparisons.

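### LENS A always precedes LENS B, so the lens effect is fully confounded with order and the paired test cannot isolate it

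*Combined protocol and SAP*

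**What the plan says.** Section 8.3 gives one order for everyone: LENS A is "fitted first to all participants, followed by" LENS B. The visit outline agrees. At the Visit 1 trial fit (8.3.1) the site removes LENS A "and insert trial toric" LENS B; LENS A is dispensed and rated at Visit 2 (8.3.2), and LENS B at Visit 3 (8.3.4).

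The design statement in Section 4 reads "This is a subject masked, interventional, prospective, direct refit, bilateral wear study". It mentions no randomisation, crossover or counterbalancing.

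One passage points the other way. Section 8.2.1 says suitable subjects are "dispensed the first pair of the assigned lens brand assigned per a determined table (Appendix 3"). That appendix is not in the text available for review.

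The alternative hypothesis (3.1) is "There is a difference in clinical performance and subjective assessments between toric lens types". Section 10.1 states: "Differences between lenses will be compared using Paired t-tests". It names the Wilcoxon signed ranks test for ordinal data and a chi-square test for lens preference. No period or sequence term appears.

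**The concern.** The primary outcome (Section 2) is a subject's own handling score on a 0-10 scale, given for two insertions that Section 8.3 places within one day. A second rating can differ from a first for reasons unrelated to the lens: practice, irritation from repeated insertion, or use of the first score as an anchor. Masking the subject to brand (8.2.6) does not hide which pair came first. The plan accepts the principle elsewhere: Section 8.3 withholds fluorescein before dispensing because it might affect later comfort ratings.

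If every subject has A first and B second, such an effect is read as a lens effect. The test may then find a difference between lenses that handle identically, or miss a real one. The preference question is exposed in the same way, since everyone tries LENS B last.

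**Working it through.** **Inputs.** From Section 10.2 and its Figure 1: two-sided α = 0.05, SD of paired differences 1.2, target difference 0.6 points, 37 completers, stated power 0.841192. The size of the order effect is not in the documents; the range 0 to 0.6 points below is an assumption.

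**1. The plan's own figure.** For a paired t-test, SE = SD/√n = 1.2/√37 = 0.1973. The noncentrality is 0.6/0.1973 = 3.04 on 36 degrees of freedom. The exact noncentral-t power is 84.1%, as stated. The other two rows of Figure 1 also reproduce (n = 34: 80.8%; n = 44: 90.0%). The sample-size arithmetic is correct.

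**2. What the paired difference estimates.** Let τ be the true lens difference (B minus A), π the effect of being second, and λ_A the carryover from A to the following lens. Under the fixed order every subject contributes

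E(B − A) = τ + π + λ_A.

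Lens and period are perfectly collinear, so a period term cannot be fitted. The bias π + λ_A does not depend on n.

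**3. Consequence for the test.** Treat the order effect as a single shift p. With no lens difference the noncentrality is p/0.1973 (for example 0.3/0.1973 = 1.52). With a true difference of 0.6 and an opposing order effect it is (0.6 − p)/0.1973.

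| Assumed order effect (points) | Chance of p ≤ 0.05, lenses identical | Power, true difference 0.6, order effect opposing |
|---|---|---|
| 0 | 5.0% | 84.1% |
| 0.1 | 7.8% | 69.4% |
| 0.2 | 16.7% | 50.5% |
| 0.3 | 31.6% | 31.6% |
| 0.4 | 50.5% | 16.7% |
| 0.6 | 84.1% | 5.0% |

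**4. Counterbalanced order.** In the A-B sequence E(B − A) = τ + π + λ_A; in the B-A sequence E(B − A) = τ − π − λ_B. Their average is τ + (λ_A − λ_B)/2, so π cancels, and carryover cancels too if it is equal for the two lenses. With a period term,

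SE = (1.2/2)·√(1/n₁ + 1/n₂), df = n − 2.

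- 18/19 subjects: SE = 0.6·√(1/18 + 1/19) = 0.1974, df 35, power 84.0%.
- 20/20 subjects: SE = 0.6·√(1/20 + 1/20) = 0.1897, df 38, power 86.9%.

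In a simulation of 100,000 trials (18/19), the type I error was 4.9%, 5.0% and 5.0% for order effects of 0, 0.3 and 0.6 points. The fixed-order paired test in the same simulation gave 4.9%, 31.4% and 84.2%.

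**The case against.** **Appendix 3 may vary the order.** Section 8.2.1 speaks of an assigned first brand, and the synopsis and Section 4 label the pairs neutrally as P1 and P2. If the table alternates the order, the confounding disappears. But it would then contradict Section 8.3 and the visit outline, both of which are visible and explicit. The text has to change either way.

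**The order effect may be small.** Subjects are adapted wearers (8.1), both lenses are trial-fitted before any handling rating visible in the plan (8.3.1), and subjects are masked. This makes a large practice effect less likely, and nothing in the documents supports the upper end of the assumed range. It does not remove anchoring or irritation, and subjects may not be habitual wearers of either study lens. The plan neither states nor supports an order effect of zero.

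**The claim is broad.** The aim also covers fit and vision, for which practice and anchoring matter less. That is fair: the named mechanisms bear on the subjects' ratings. Handling is the primary outcome, however, and the collinearity applies to every paired comparison.

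**A crossover assumes no differential carryover.** True, and no washout is visible (steps are redacted). But the fixed order needs π + λ_A to be zero, whereas the crossover needs only λ_A = λ_B. For two lenses of the same material, each worn for 15 minutes, the second is the milder assumption.

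**Conclusion.** The concern holds. As written, the primary comparison estimates lens effect plus order effect, and no analysis or sample size can separate them. It answers the lens question only on the unstated assumption that order has no effect. The existence of the confounding follows from the design alone. Its size is unknown: the false-positive rates of 7.8% to 84.1% are illustrations for assumed order effects of 0.1 to 0.6 points, using the plan's SD and 37 completers. Because the design targets only 0.6 points on a 0-10 scale, an order effect of 0.2 or 0.3 points is already enough to undermine the test. The defect cannot be repaired after data collection, so it must be corrected before enrolment.

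**What to change.** - **Order.** Randomise 1:1 to A-B or B-A, for example 20/20 in small permuted blocks. Hold the list in Appendix 3, or confirm that Appendix 3 already does this. For consistency, use the same order at the Visit 1 trial fits; this is secondary, since no handling rating is visible there.
- **Text.** Replace the fixed-order sentence in 8.3, retitle 8.3.2 to 8.3.5 as first lens and second lens, and bring 8.2.1, Section 4 and the synopsis into line.
- **Analysis.** In 10.1, make the primary comparison period-adjusted: compare within-subject period differences between the two sequences, or fit a mixed model with lens and period. An unadjusted paired test would leave the order effect in the variance: at 0.3 points the SD of differences rises from 1.2 to √(1.2² + 0.3²) = 1.24. Analyse preference by sequence as well. State the assumption of equal carryover.

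**Cost.** A randomisation list, relabelled forms and one degree of freedom. Power with 37 completers is 84.0% against 84.1%. No extra subjects, visits or lenses are needed.

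If data have already been collected in the fixed order, the report should say that the estimated difference includes any order effect.
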